4.3 Rationale for 2 Study Populations

The 2 SS populations, which distinguish patients with predominantly glandular dysfunction and those with both glandular dysfunction and systemic manifestations, represent subsets with significant unmet need that require different endpoints to assess efficacy. The ESSDAI is a validated instrument to assess systemic disease activity (Seror et al, 2010). The ESSPRI uses a 0-10 numerical analog scale, one for the assessment of each of the 3 domains of SS symptoms: dryness, fatigue, and pain (articular and/or muscular).

Population #1 with moderate to high systemic activity, defined by ESSDAI ≥ 5, has been the focus of many recent SS trials. About 15-20% of SS patients present with systemic manifestations beyond the commonly affected exocrine glands (salivary and ocular). These manifestations most commonly include arthritis, lung disease, renal disease, vasculitis, and peripheral neuropathies, as well as autonomic nervous system dysfunctions that accompany glandular involvement. Moderate to high disease activity may lead to physical dysfunction and poor QoL, as well as dysfunction of the affected organ(s). In addition, patients with pSS who have moderate to high disease activity are more prone to developing B-cell lymphoma, which in turn, has been associated with an increased risk of death (Brito-Zeron et al, 2016). Despite the increased number of trials, no biologics or DMARDs have been shown to be efficacious in significantly reducing SS systemic disease activity.

Population #2 comprises SS patients with exocrine dysfunction and severe subjective symptoms defined by an ESSPRI score of \geq 5, considered as the cut-off point for "unsatisfactory symptom state" (Seror et al, 2016a) but lower systemic disease activity. This population represents a large subset of SS patients who have been excluded from recent trials despite the substantial disease burden and overall unacceptable health status.

The Eligibility Criteria related to the 2016 ACR/EULAR Classification Criteria for SS for both Population #1 and Population #2 and the disease activity data for the ESSDAI score for

Population #1 will be reviewed by the Sponsor/designee prior to enrollment to confirm subject eligibility.

4.4 Rationale for Primary Endpoint Selection

VIB4920 targets B cell-mediated autoimmune diseases and has been shown in the phase 1b RA trial to significantly decrease inflammatory markers and inflammatory cytokines (eg, CRP, IL-6) that are known to be associated with systemic, glandular, and subjective manifestations of SS, including pain, fatigue, and dryness. Thus, VIB4920 has the potential to improve inflammatory manifestations of SS and also to alleviate the most prominent features that lead to the unsatisfactory symptom state observed in SS.

The primary endpoints have been selected for each of the 2 SS Populations in this study: Change from baseline in ESSDAI for Population #1 and Change from baseline in ESSPRI for Population #2. Both are validated measures of objective (ESSDAI) and subjective (ESSPRI) disease activity in SS and have been used widely in SS clinical trials.

5 POPULATION

5.1 Inclusion and Exclusion Criteria

The study medical review (MR) team will review the Eligibility Criteria related to the 2016 ACR/EULAR Classification Criteria for SS and ESSDAI score to confirm patient eligibility for Population #1 and will review items related to the 2016 ACR/EULAR Classification Criteria for SS for Population #2 (see Section 6.1 for details).

5.1.1 Inclusion Criteria for Population #1

To be included in Population #1 of this study, each individual must satisfy all the following criteria:

- 1. Adults, 18 years or older at time of informed consent (the minimum age for adult participants can be higher than 18 years in countries with different regulations).
- 2. Diagnosed with SS by meeting the 2016 ACR/EULAR Classification Criteria.
- 3. Have an ESSDAI score of ≥ 5 at screening; the following domains will be scored but they will not contribute to the minimum ESSDAI score of 5 required for inclusion: Peripheral nervous system, Central nervous system, and Pulmonary.
- 4. Positive for either anti-Ro autoantibodies or RF, or both at screening, as per the definition of the standard central laboratory test.
- 5. Written informed consent and any locally required authorization (eg, Health Insurance Portability and Accountability Act in the United States, European Union [EU] Data Privacy Directive in the EU) obtained from the subject/legal representative prior to performing any protocol-related procedures, including screening evaluations.
- 6. Females of childbearing potential who are sexually active with a nonsterilized male partner must use a highly effective method of contraception from signing the informed consent form (ICF), and must agree to continue using such precautions through the end of

the study follow-up; cessation of contraception after this point should be discussed with a responsible physician. Highly effective methods of contraception include:

- combined (estrogen and progestogen containing) hormonal contraception associated with inhibition of ovulation:
- oral
- intravaginal
- transdermal
- progestogen-only hormonal contraception associated with inhibition of ovulation:
- oral
- injectable
- implantable
- intrauterine device (IUD)
- intrauterine hormone-releasing system (IUS)
- bilateral tubal occlusion
- vasectomized partner
- sexual abstinence

Sexual abstinence is considered a highly effective method only if it is the preferred and usual lifestyle of the subject and the subject agrees to refrain from heterosexual intercourse from signing the ICF through the end of the study follow-up. Periodic abstinence, the rhythm method, and the withdrawal method are not acceptable methods of contraception. A recommendation that the female partners (of childbearing potential) of male study participants should use a highly effective method of contraception other than a barrier method is made.

- Females of childbearing potential are defined as those who are not surgically sterile (surgical sterilization includes bilateral tubal ligation, bilateral oophorectomy, or hysterectomy) or those who are not postmenopausal (defined as 12 months with no menses without an alternative medical cause).
- Vasectomized partner is a highly effective birth control method provided that
 partner is the sole sexual partner of the woman of childbearing potential trial
 participant and that the vasectomized partner has received medical assessment of
 the surgical success.
- 7. Nonsterilized male subjects who are sexually active with a female partner of childbearing potential must use a condom with spermicide from Day 1 through the end of the study.
- 8. Meets all of the following tuberculosis (TB) criteria:
 - a. No history of latent or active TB prior to screening, with the exception of latent TB with documented completion of appropriate treatment.
 - b. No signs or symptoms suggestive of active TB from medical history or physical examination.

- c. No recent (\leq 12 weeks of screening) close contact with a person with active TB (close contact is defined as \geq 4 hours/week OR living in the same household OR in a house where a person with active TB is a frequent visitor).
- d. Negative Interferon Gamma Release Assay (IGRA) test result for TB obtained within 12 weeks prior to randomization. Subjects with an indeterminate test result can repeat the test, but if the repeat test is also indeterminate, they are excluded.
- e. A chest radiograph (obtained during the screening period or any time within 12 weeks prior to signing of the ICF) with no evidence of current active TB or other infection, or old active TB, malignancy, or clinically significant abnormalities suggesting an active process (unless due to SS).

5.1.2 Exclusion Criteria for Population #1

If an individual for Population #1 meets any of the following criteria, he or she is ineligible for this study:

- 1. Patients with medical history of confirmed deep venous thrombosis or arterial thromboembolism within 2 years of signing the ICF.
- 2. Patients with risk factors for venous thromboembolism or arterial thrombosis (eg, immobilization or major surgery within 12 weeks before screening), prothrombotic status (including, but not limited to, congenital or inherited deficiency of antithrombin III, protein C, protein S, or confirmed diagnosis of catastrophic antiphospholipid syndrome).
- 3. Patients requiring treatment with anticoagulant drugs (clopidogrel, prasugrel, warfarin, low molecular weight heparin, others). Low-dose aspirin treatment (up to 325 mg/day) is allowed.
- 4. Concomitant polymyositis or dermatomyositis or systemic sclerosis.
- 5. Active malignancy or history of malignancy, except as follows:
 - a. In situ carcinoma of the cervix treated with apparent success with curative therapy > 12 months prior to screening; or
 - b. Cutaneous basal cell carcinoma following apparently curative therapy.
- 6. Subjects who are pregnant or lactating or planning to become pregnant during the duration of the study.
- 7. Subjects who have a positive test for, or have been treated for hepatitis B, hepatitis C, or HIV infection.
 - Regarding hepatitis B, positive test for chronic hepatitis B infection at screening, defined as either (1) positive hepatitis B surface antigen (HBsAg) or (2) a positive hepatitis B core antibody (anti-HBc).
- 8. Subjects with:
 - a. A history of more than one episode of herpes zoster and/or opportunistic infections in the last 12 months, with the exception of oral candidiasis, vaginal candidiasis, and cutaneous fungal infections.

- b. Active viral, bacterial or other infections requiring systemic treatment at the time of screening or through randomization, or history of more than 2 infections requiring IV antibiotics within 12 months prior to signing the ICF.
- c. Epidemiologic risk of COVID-19 (recent exposures, high-risk housing) and for health-related risk of COVID-19 severity based on current understanding of risk factors for severe disease when making a decision regarding the individual subject's risk of participation. Subjects who have active COVID-19 infection or disease or other significant infection, or, in the judgment of the investigator, who may be at unacceptable risk of COVID-19 or its complications should not be randomized.
- d. A documented positive SARS-CoV-2 test within 2 weeks prior to randomization. Subjects with a positive test for SARS-CoV-2 may be rescreened at least 2 weeks after a positive test if asymptomatic and at least 3 weeks after symptomatic COVID-19 illness.
- 9. Subjects with known history of severe allergy or reaction to any component of the IP formulation or to any other biologic therapy.
- 10. Subjects with any severe cardiovascular, respiratory, endocrine, gastrointestinal, hematological, neurological, psychiatric, or systemic disorder or any other condition that in the opinion of the Investigator, would place the subject at unacceptable risk of complications, interfere with evaluation of the IP or confound the interpretation of subject safety or study results.
- 11. Subjects who are unable or unwilling to comply with protocol requirements (eg, active drug or alcohol abuse).
- 12. Subjects who have received live (attenuated) vaccine within the 4 weeks prior to ICF signature.
- 13. Last administration of experimental biologic (other than those listed in Point 14) or oral agents < 3 months or 5 half-lives before randomization.
- 14. Subjects who have had previous treatment with any biologic B-cell-depleting therapy (eg, rituximab, ocrelizumab, or ofatumumab) within 12 months or other B-cell targeting therapy (eg, belimumab) < 3 months before randomization.
- 15. Injectable corticosteroids (including intra-articular) or treatment with > 10 mg/day dose oral prednisone or equivalent within 6 weeks prior to randomization. Concomitant treatment with oral corticosteroids ≤ 10 mg/day prednisone or equivalent is permitted provided that the dose is stable ≥ 2 weeks prior to screening through randomization (Day 1) and is expected to remain stable for the duration of the treatment period. Inhaled or topical corticosteroids given for asthma, chronic obstructive pulmonary disease or dermatological conditions are allowed provided doses are expected to be stable during the study.
- 16. Subjects treated with systemic corticosteroids for indications other than SS, RA, and SLE for more than a total of 2 weeks within 24 weeks prior to screening visit.
- 17. Use of the following medications:

- a. Antimalarials (eg, chloroquine, hydroxychloroquine, quinacrine) if they have been initiated or if the dose has changed within 8 weeks prior to signing the ICF or during the screening period.
- b. MTX, if the dose is > 20 mg/week; or if there is any change or initiation of new dose within 4 weeks prior to signing the ICF through randomization (Day 1), or if there has been any change in route of administration.
- c. Azathioprine (AZA), if the dose is > 150 mg/day and there is any change or initiation of new dose within 4 weeks prior to signing the ICF through randomization (Day 1) and any change in route of administration.
- d. Leflunomide, if the dose is >20 mg/day; or if there is any change or initiation of new dose within 4 weeks prior to signing the ICF through randomization (Day 1).
- e. Mycophenolate mofetil (MMF), if the dose is >2g/day; or if there is any change or initiation of new dose within 4 weeks prior to signing the ICF through randomization (Day 1).
- f. Any other DMARD, immunosuppressant, or antiproliferative agents, if last dose was taken within:
 - 4 weeks prior to signing ICF or
 - Drug-specific 5 half-lives elimination period (if longer than 4 weeks).
- g. Any medication that, in the opinion of the Investigator, would interfere with evaluation of the IP or interpretation of subject safety or study results.
- h. Any increase or initiation of new doses of cevimeline or pilocarpine and cyclosporine eye drops (Restasis®) within 2 weeks prior to signing the ICF through randomization (Day 1).
- 18. Subjects who have received previous treatment with anti-CD40L compounds at any time before screening.
- 19. Subjects with blood tests, at screening, of any of the following:
 - Aspartate aminotransferase (AST) > 2 x upper limit of normal (ULN)
 - Alanine aminotransferase (ALT) > 2 x ULN
 - Total bilirubin (TBL) > 2 x ULN
 - Hemoglobin < 75 g/L
 - Neutrophils $< 1.0 \times 109/L$
 - Platelets < 100 x 109/L
 - Prothrombin or partial thromboplastin time (PTT) > ULN

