3.4.4 Prior and Concomitant Medications

Number (%) of subjects who receive prior medications and concomitant medications during Stage I and during Stage II + Off-treatment follow-up period will be summarized by world health organization (WHO) Drug dictionary Anatomical Therapeutic Chemical (ATC) category and PT. At each level of summarization, a subject is counted once if he/she reported one or more medications at that level. The summary of prior medications and concomitant medications during Stage I will be based on the safety analysis set. The summary of concomitant medications during Stage II + Off-treatment follow-up period will be based on the cross-over analysis set.

The prior and concomitant medications are defined as below.

- Prior medications are defined as medications with a stop date occurring before the first IP administration date.
- Concomitant medications during Stage I are defined as follows:
 - Medications with a start date before the Day 169 IP administration date and stop date on or after the first IP administration date for subjects entering Stage II.
 - Medications with a stop date on or after the first IP administration date for subjects not entering Stage II.

• Concomitant medications during Stage II + Off-treatment follow-up period are defined as medications with a stop date on or after the Day 169 IP administration date.

Use of disease-related medications at baseline, defined as all disease-related medications with an intake at the date of first dose of IP (ie, start date on or before the date of first dose and end date on or after date of first dose or ongoing) will be summarized for the full analysis set. The number and percentage of subjects who receive rescue medication during Stage I and during Stage II + Off-treatment follow-up period will also be summarized for the full analysis set and cross-over analysis set respectively.

Rescue medications for population #1 are listed below:

- Azathioprine (AZA) > 150 mg/day, methotrexate (MTX) > 20 mg/week, leflunomide >20 mg/day, mycophenolate mofetil (MMF) > 2gm/day OR any increase from baseline (including initiation of treatment)
- Any increase from baseline in anti-malarial (including initiation of treatment)
- Initiation of any new conventional disease-modifying anti-rheumatic drug (cDMARD)
- Oral prednisone > 10 mg/day OR any increase from baseline (including initiation of treatment)
- Intramuscular, IV, or intraarticular corticosteroids

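### The azathioprine exclusion for Population #1 (Protocol 5.1.2, item 17c) joins its conditions with *and* where the matching rules use *or*, so as written it leaves out most of the use it was probably meant to bar (minor).

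*Protocol*

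**What the plan says.** Item 17 of the Population #1 exclusion criteria (Protocol 5.1.2) sets limits on background immunosuppressants.

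- **Azathioprine (17c):** "Azathioprine (AZA), if the dose is > 150 mg/day and there is any change or initiation of new dose within 4 weeks" before consent, continuing "through randomization (Day 1) and any change in route of administration".
- **Methotrexate (17b):** "MTX, if the dose is > 20 mg/week; or if there is any change or initiation of new dose within 4 weeks". A route change follows as a further alternative, also joined by *or*.
- **Leflunomide (17d):** "Leflunomide, if the dose is >20 mg/day; or if there is any change or initiation of new dose within 4 weeks".
- **Mycophenolate (17e):** "Mycophenolate mofetil (MMF), if the dose is >2g/day; or if there is any change or initiation of new dose within 4 weeks".

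Item 17f is a washout for agents other than those already named, so it does not reach azathioprine. Item 17g is a catch-all: "Any medication that, in the opinion of the Investigator, would interfere with evaluation of the IP or interpretation of subject safety or study results".

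After randomisation, Protocol 7.4.2 restricts azathioprine above 150 mg/day or any increase from baseline. It requires the Medical Monitor to be notified and makes the subject a non-responder for binary assessments. Protocol 7.4.3 defines rescue as starting, or raising the dose of, a restricted drug. The SAP's own rescue list (3.4.4) opens with "Azathioprine (AZA) > 150 mg/day, methotrexate (MTX) > 20 mg/week, leflunomide >20 mg/day" and gives any increase from baseline as an alternative. SAP 3.5.1.3 removes data collected after rescue, as defined in 3.4.4, from the primary analysis. SAP 3.5.2.1 requires responders to be free of rescue.

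**The concern.** Nothing in the visible text explains why azathioprine should have a looser entry rule than the three drugs listed beside it. The later sections treat a dose above 150 mg/day, or any increase, as something to be controlled. The *and* in 17c looks like a drafting slip, but it sits in an operative eligibility rule applied at approximately 70 sites. A site that reads it literally and a site that reads it for intent would classify the same patient differently.

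Two things are at stake. First, subjects can enter on azathioprine that was started or changed shortly before Day 1, which the sibling rules prevent for the other drugs. Second, subjects can enter on a dose that the SAP's rescue list names as a fixed threshold. If that list is applied literally, unchanged background treatment counts as rescue from Day 1. The subject then contributes no post-baseline data to the primary mixed model and cannot be a responder.

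**Working it through.** **Step 1: what 17c excludes.** Take three yes/no conditions: dose above 150 mg/day (H), start or change within the window (C), route change (R). As written, 17c excludes when H and C and R all hold. The 17b structure excludes when any one holds.

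| H | C | R | 17c as written | 17b structure |
|---|---|---|---|---|
| no | no | no | eligible | eligible |
| no | no | yes | eligible | excluded |
| no | yes | no | eligible | excluded |
| no | yes | yes | eligible | excluded |
| yes | no | no | eligible | excluded |
| yes | no | yes | eligible | excluded |
| yes | yes | no | eligible | excluded |
| yes | yes | yes | excluded | excluded |

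As written, 1 of 8 combinations is excluded; under the 17b structure, 7 of 8. If the route clause is ignored, 2 of 8 are excluded (H and C). That closes the high-dose, recently changed gap. Stable high-dose use and recently changed lower-dose use remain eligible, because the first *and* alone creates those gaps.

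**Step 2: the plan's own power figure.** Inputs from Protocol 10.3: 36 per arm, difference 3.0, SD 5, two-sided alpha 0.10, two-sample t-test.

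- SE = 5 × √(2/36) = 1.179
- Noncentrality = 3/1.179 = 2.546, with 70 degrees of freedom
- Power from the noncentral t = 0.8095, or 81.0%, consistent with the stated 80%
- 90% CI half-width = 1.667 × 1.179 = 1.96, consistent with the stated minimum detectable difference of 2.0

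**Step 3: the conditional loss.** The documents do not give azathioprine use. Assume k subjects per arm enter on unchanged azathioprine above 150 mg/day and the SAP list is applied literally. Then n = 36 − k, SE = 5 × √(2/n), half-width = t(0.95, 2n − 2) × SE, and SE growth = √(36/n).

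| k per arm | Share of 36 | SE | SE growth | 90% half-width | Power, k lost in each arm | Power, k lost in one arm only |
|---|---|---|---|---|---|---|
| 0 | 0% | 1.179 | 0% | 1.96 | 81.0% | 81.0% |
| 1 | 2.8% | 1.195 | 1.4% | 1.99 | 80.0% | 80.5% |
| 2 | 5.6% | 1.213 | 2.9% | 2.02 | 78.9% | 79.9% |
| 3 | 8.3% | 1.231 | 4.4% | 2.05 | 77.8% | 79.4% |

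The SE, SE growth and half-width columns are for k lost in each arm. At k = 1 in each arm, power is 0.7996, which is 80% only after rounding.

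**Step 4: the responder endpoints.** Forced non-responders stay in the denominator. With k in each arm, and p₁ and p₀ the response rates in the remaining subjects, the observed difference is (36 − k)/36 × (p₁ − p₀). That is 97.2%, 94.4% or 91.7% of the difference for k = 1, 2 or 3. The comparison is pulled toward no difference.

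**Step 5: which analyses are affected.** On the literal reading, the primary mixed model loses the subject. The first sensitivity analysis in SAP 3.5.1.5 imputes the worst score, baseline included, so the subject can show no improvement. The second sensitivity analysis and the time-adjusted AUC analysis keep the observed data.

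**The case against.** The strongest reply is that this is editorial. The intent can be recovered from 17b, 17d and 17e and from Protocol 7.4.2, and a rule that needs all three conditions at once is implausible. Sites also know that azathioprine above 150 mg/day after randomisation means notifying the Medical Monitor, which discourages enrolling such a subject. Protocol 6.3 requires the medical review team to confirm eligibility before randomisation, and Protocol 6.1 lets that team look at concomitant medication as appropriate.

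Much of this stands. It is why the point is minor, and why it would be wrong to say that 17g is the only check. But Protocol 5.1 directs the team's eligibility review at the classification criteria and the ESSDAI score, and no text gives the team an azathioprine limit to apply. Inferring intent is not a rule.

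A reader might go further and infer that subjects on stable high-dose azathioprine will be dropped from the primary analysis. The documents do not support that. Such a subject must first be enrolled, and the SAP list must then be programmed literally. Protocol 7.4.3 limits rescue to initiation or increase, and SAP 3.4.4 summarises baseline treatment separately: "Use of disease-related medications at baseline, defined as all disease-related medications with an intake at the date of first dose of IP". On the other side, SAP 3.5.1.3 points to the SAP's own list, which is not a straight copy of the protocol's (leflunomide is capped at 20 mg/day in the SAP and 40 mg/day in Protocol 7.4.2). Protocol 7.4.3 therefore cannot simply be assumed to govern. What is shown is an ambiguity.

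A reader might also infer bias between arms in the primary comparison. The baseline regimen is fixed before randomisation, so the loss there is of information. Attenuation applies to the responder comparison.

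**Conclusion.** Item 17c is wrong as written, and the matter is minor. No other Population #1 criterion sets an azathioprine dose or stability limit; 17g is discretionary and medical review is a partial safeguard. Population #2 is unaffected, because its criteria impose a washout for azathioprine.

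The entry defect follows from the text alone. The analysis consequence rests on two assumptions: that someone is enrolled on azathioprine above 150 mg/day, and that SAP 3.4.4 is read as counting an unchanged dose as rescue. Under both, 0 to 3 subjects per arm take power from 81.0% to 77.8% and widen the 90% half-width from 1.96 to 2.05 points. The true number may be zero. These figures use the protocol's t-test with SD 5; the planned baseline-adjusted mixed model may differ. No size is claimed for lower-dose subjects with a recent start or change, and they do not meet the rescue list unless the dose later rises.

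**What to change.** **Main change, if enrolment is open.** At the next amendment, give 17c the structure of 17b: exclude if azathioprine exceeds 150 mg/day; or if it was started or its dose changed between 4 weeks before consent and Day 1; or if the route changed. The documents do not say whether enrolment is open. If it has closed, this change has no value.

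**Supporting change, before unblinding.** In SAP 3.4.4, state that azathioprine rescue means initiation or an increase from the subject's own baseline regimen, in line with Protocol 7.4.3, and that this definition also applies to the responder endpoints. It protects anyone already randomised under the present 17c; if there is no such subject, no result changes. Leave the Medical Monitor notification in Protocol 7.4.2 as it is, since a dose above 150 mg/day still merits notice.

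**Cost.** The SAP edit is one sentence and needs no new data. The 17c change needs ethics approval before implementation at approximately 70 sites, and possibly reconsent, so it should be bundled with other changes. The downside is paperwork only.
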